2.8.2.6 Generalised Estimating Equations

In addition, a model fitting the development of geographic atrophy in the first 12-month period or the second 12-month period may be fitted to provide one analysis of the newly developed GA over time. This analysis would be undertaken using a generalised estimating equation (GEE) logistic regression.

Absence/Presence of IRF and/or SRF may also be analysed using a GEE logistic regression.

2.8.2.7 Analysis of Binomial Data

The mean number of injections over the 24-month period will be analysed using a Negative Binomial model for count type data. The number of injections will be the outcome variable and treatment as a class variable. The logarithm length of time each subject is in the study up to their 24-month visit will be used as an offset variable. The injection frequency (per year) and the difference between injection frequencies (ratio) will be obtained for each treatment group along with the corresponding 95% confidence intervals and p-values. The model may be expanded to cater for other time points such as 12 months or separate analyses.

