Patients withdrawn from the study prior to completion of the 24 month assessment visit will be asked to return for an Early Discontinuation evaluation 30 days +/- 7 days following their last study visit.

SCN = Screening, BSL = baseline, INITIAL 3 TR. = Initial 3 treatments at 4 weekly intervals both arms, Flexible interval Tr = treatment intervals will differ based on arm and disease activity, Pr. EP = Primary Endpoint, EOS= End of study.

Figure 1 Study design

2 Project standards

Treatment groups for the analysis

The group labels for the 2 treatment groups for the analysis are: “Intensive” (Group I) and “Relaxed” (Group II).

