2.6 Study medication

The following summaries will be presented for the injections in the study eye and the fellow treated eye using the Safety Set:

- Duration of Exposure
 - Descriptive statistics (mean, median, standard deviation, minimum and maximum) will be presented using days as the unit.
- The number of ranibizumab injections presented by treatment group in frequency tables by visit and cumulatively.

Analyses of the treatment exposure and treatment patterns of the two alternative treatment regimens over 24 months include:

- Treatment frequency
- Total number of injections
- Reason for interval decision (as defined within disease activity for each arm)

The number of injections administered per patient for injections in the study eye will be summarized. Both the frequency distribution (number of patients with 1 injection, number of patients with 2 injections, on up to the maximum number of injections for any one patient for the given treatment period) and summary statistics for the number of injections per patient will be presented.

Additionally, a listing of summarized dosing parameters (e.g., total number of injections in the study eye) will be provided. A listing will also be provided detailing data related to the study observation period.

Furthermore, to assess visit/treatment frequency and average visit/dosing interval, the following summaries will be provided (within the FAS)

- The number (%) of patients by the maximum visit interval (4, 6, 8, 10 and 12 weeks); a visit interval is defined as the difference of the visit week number as from the visit date. E.g. if the first visit to be considered is recorded as Week 16 visit and the next visit is recorded as Week 22 visit, then the visit interval is 6 weeks; the maximum visit interval is evaluated on a patient level, i.e. the longest visit interval within the study for each patient.

- The number (%) of patients for whom the visit interval was never decreased, decreased once, decreased two times; The decrease of the visit interval is based on a comparison with the previous visit interval. E.g. if the previous visit interval was 8 weeks and the current visit interval is 6 weeks (4 weeks), then the visit interval was decreased by 2 weeks (4 weeks).
- The number (%) of patients by breakpoint interval (4, 6, 8, 10 and 12 weeks); (the injection interval equals the visit interval)
- The number (%) of patients by the number of times the patient returned to monthly injections.

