2.8.1 Variables

The primary efficacy variable and key secondary variables are:

- Mean change in BCVA from baseline to month 24
- Mean change in BCVA from baseline to month 12
- Mean change in central retinal thickness from baseline to month 12 and month 24
- Number of injections from baseline to month 12 and 24

The additional secondary variables are:

- Mean change in area of new and existing geographic atrophy from baseline to month 12 and 24.

Patients at sites where autofluorescence can be undertaken will be assessed for the presence of geographic atrophy at Baseline, visit 4 (week 8) and then again at the 12 and 24 month visits. If present, the area of geographic atrophy will be estimated.

- New Geographic Atrophy at month 12 and month 24^a (Yes, No)
 - Change in area of geographic atrophy from the visit where geographic atrophy was first present
- Intra-retinal (IRF) and Sub-retinal fluid (SRF) (present/absent)

At each relevant assessment visit, the patient is examined for the presence/absence of IRF and SRF by the central reading centre as per the definitions for their treatment arm.

- The proportion of patients showing no IRF and SRF at month 2, 12 and 24
- Proportion of patients showing greater than or equal to 15 letters (EDTRS) gain and less than 15 letters loss from baseline to month 24.
- Proportion of patients with SRF as assessed by the [REDACTED] CRC and IRF as assessed by Investigators at baseline who do not resolve their SRF and IRF by Month 24

The remaining exploratory variables are:

- Proportion of patients with a) SRF, b) IRF, c) both SRF and IRF, d) neither SRF and/or IRF at baseline, month 2, 12 and 24
- Proportion of patients with $\geq 6/12$ visual acuity at baseline, month 12 and month 24
- Proportion of patients with 6/60 or worse visual acuity at baseline, month 12 and 24
- The proportion of patients with IRF and SRF at baseline who never resolve either their IRF or SRF at any visit up to Month 2, 12 and 24.
- Proportion of patients with SRF at baseline who never resolve their SRF at any visit up to Month 2, 12 and 24 (irrespective of their IRF)
- Proportion of patients with IRF at baseline who never resolve their IRF at any visit up to Month 2, 12 and 24 (irrespective of SRF)

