2.8.2 Statistical hypothesis, model, and method of analysis

Statistical methodologies for efficacy variables are detailed in Table 2.8.2-1 (Primary efficacy), Table 2.8.2-2 (Secondary efficacy) and Table 2.8.2-3 (Exploratory efficacy).

Table 2.8.2-1 Primary and Key Secondary Efficacy Analyses

Study Endpoint	Method of Analysis
Mean change in BCVA from baseline to months 12 and 24	1. Mixed Modelling (Refer to Section 2.8.2.5) 2. Summary statistics of change from baseline will be presented.
Mean change in central retinal thickness (CRT) from baseline to months 12 and 24	1. Mixed Modelling (Refer to Section 2.8.2.5) 2. Summary statistics of change from baseline will be presented.
Mean number of injections from baseline to months 12 and 24	1. Binomial Model 2. All data will be listed.

Table 2.8.2-2 Additional Secondary Efficacy Analyses

Study Endpoint	Method of Analysis
Geographic Atrophy from Baseline to Month 12 / 24 (newly developed geographic atrophy between baseline and Month 24 (Yes/No))	1. Logistic regression model (Refer to Section 2.8.2.8) 2. Survival Analysis (Refer to Section 2.8.2.10)
Geographic Atrophy from Baseline to Month 12 / 24 (Change in area of geographic atrophy from the visit where geographic atrophy was first present)	1. Mixed Modelling (Refer to Section 2.8.2.8)
Proportion of patients showing greater than or equal to 15 letters (EDTRS) gain from baseline to month 24	1. Logistic regression model (Refer to Section 2.8.2.8)
Proportion of patients showing less than 15 letters loss from baseline to month 24	1. Logistic regression model (Refer to Section 2.8.2.8)
Proportion of patients showing no IRF and SRF at month 2, 12 and 24	1. Logistic regression model (Refer to Section 2.8.2.8)

Table 2.8.2-3 Exploratory Efficacy Analyses

Study Endpoint	Method of Analysis
Proportion of patients with SRF, as assessed by the █████ CRC, and IRF, as assessed by investigators at Baseline, who do not resolve their SRF and IRF by Month 24	1. Logistic regression model (Refer to Section 2.8.2.8)
The proportion of patients with a) SRF b) IRF c) both SRF and IRF d) neither SRF or IRF at baseline, 2, 12, 24 months	1. Logistic regression model (Refer to Section 2.8.2.8)

Proportion of patients with SRF at baseline who never resolve their SRF at any visit up to Month 2, 12 and 24 (irrespective of their IRF)	1. Logistic regression model (Refer to Section 2.8.2.8)

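### The negative binomial model for injection counts cannot represent variance below the mean, which is probable at Month 12, so that confidence interval would probably be too wide

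*SAP*

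**What the plan says.** SAP 2.8.1 places "Number of injections from baseline to month 12 and 24" among the primary and key secondary variables. Table 2.8.2-1 repeats the endpoint, "Mean number of injections from baseline to months 12 and 24", with a method cell that reads only Binomial Model.

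The method itself is in SAP 2.8.2.7, where the mean count over 24 months "will be analysed using a Negative Binomial model for count type data". Exposure enters as follows: "The logarithm length of time each subject is in the study up to their 24-month visit will be used as an offset variable". For the first year the text is permissive: "The model may be expanded to cater for other time points such as 12 months or separate analyses". Table 14.2-9 in the table shells is firmer. Its title applies negative binomial regression to Months 12 and 24, although its footnote, like the SAP, runs the offset to the 24-month visit. The shell has a dispersion row.

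Neither document states a dispersion check, a robust or scaled variance, or a fallback model for this analysis. The robust standard error in SAP 2.8.2.8 belongs to a different model, for repeated binary fluid data.

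Two passages describe the schedule that generates the counts. The legend to Figure 1 of the SAP gives "Initial 3 treatments at 4 weekly intervals both arms". SAP 2.6 lists the intervals: "The number (%) of patients by the maximum visit interval (4, 6, 8, 10 and 12 weeks". SAP 2.6 also assigns injections given on or after the Month 12 visit to year 2.

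**The concern.** The negative binomial has variance = mean + k × mean², with k ≥ 0. It can absorb extra variation but cannot describe counts that vary less than a Poisson variable. A schedule with a fixed loading phase and a floor and ceiling on the interval produces regular counts, and over one year there is little room for patients to diverge. If the variance falls below the mean, k is estimated at zero and the reported standard error is the Poisson one, which is then too large.

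Injection number is the plan's measure of treatment burden, and the natural place for a relaxed regimen to show an advantage. An inflated standard error could leave a real first-year reduction reported as not shown, and would misstate its precision in any case.

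**Working it through.** **Inputs.** From the documents: three injections at weeks 0, 4 and 8; later intervals of 4, 6, 8, 10 or 12 weeks; year 1 ends before the Month 12 visit (week 52); 165 patients per arm (SAP 2.12); two-sided 95% intervals (SAP 2.1). There is no injection mean, SD, dispersion or power to reproduce; the only worked calculation in the plan is the BCVA sample size. The mixes of intervals below are therefore assumptions, as are the two patterns: direct (the interval applies straight after loading) and stepped (it lengthens by 2 weeks at a time).

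**Step 1: range of counts.** Injections before week 52 at intervals 4/6/8/10/12 are 13/10/8/7/6 (direct) or 13/10/8/7/7 (stepped). Before week 104 they are 26/18/14/12/10 (direct).

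**Step 2: what the range forces.** A variable on [a, b] with mean m has variance at most (m − a)(b − m).
- Range 6 to 13: the maximum variance/mean is 19 − 2√78 = 1.34, and the bound exceeds 1 for means between 9 − √3 = 7.27 and 9 + √3 = 10.73. Under-dispersion is not forced.
- Range 7 to 13: the maximum is 20 − 2√91 = 0.92. Under-dispersion is forced for completers who keep to schedule.

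**Step 3: variance/mean (V/M) under assumed mixes.** Shares are listed for intervals 4/6/8/10/12. Example, equal shares, direct, year 1: mean = 44/5 = 8.8; variance = 418/5 − 8.8² = 6.16; V/M = 0.70.

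| Mix (%) | Month 12 direct | Month 12 stepped | Month 24 direct | Month 24 stepped |
|---|---|---|---|---|
| Equal, 20 each | 0.70 | 0.58 | 2.00 | 1.65 |
| Central, 5/25/40/25/5 | 0.30 | 0.28 | 0.82 | 0.62 |
| Long, 10/15/20/20/35 | 0.59 | 0.43 | 1.66 | 1.34 |
| Short, 35/20/20/15/10 | 0.70 | 0.63 | 2.04 | 1.72 |
| U-shaped, 35/10/10/10/35 | 1.02 | 0.77 | 2.88 | 2.44 |
| Half 4-week, half 12-week | 1.29 | 0.90 | 3.56 | 3.04 |

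**Step 4: effect on the interval.** With n per arm, and mean m and variance v in each arm, the true SE of the log rate ratio is √(2v/(n m²)). At k = 0 the model gives √(2/(n m)). The ratio is √(m/v).
- Equal, direct: model √(2/(165 × 8.8)) = 0.0371; true √(2 × 6.16/(165 × 8.8²)) = 0.0311; ratio 1.20 (stepped 1.32).
- Central, direct (m = 8.4, v = 2.54): 0.0380 against 0.0209; ratio 1.82 (stepped 1.90).
- U-shaped: 1.00 direct, 1.14 stepped. Half and half: 1.00 direct, 1.05 stepped.

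Negative binomial fits to simulated data at 165 per arm agree. At Month 12 the model SE over the empirical SE was about 1.15 (equal, direct) and 1.8 to 1.9 (central, direct; coverage 100%). At Month 24 the over-dispersed mixes gave ratios of 0.88 to 1.04 and coverage of 92 to 97%; only the central mix was too wide (1.1 to 1.3). Dropout of 15% changed little.

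**Step 5: power.** Take a true 8% first-year reduction, −ln 0.92 = 0.0834.
- Equal, direct: with the correct SE, Φ(0.0834/0.0311 − 1.96) = 77%; with the model SE, Φ((0.0834 − 1.96 × 0.0371)/0.0311) = 63%.
- Central, direct: 98% against 67%.

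The reduction detectable with 80% power is 1 − exp(−(1.96 × model SE + 0.84 × true SE)). For equal shares this is 9.4% instead of 8.3%, or 0.83 against 0.73 injections. For the central mix it is 8.8% instead of 5.7%, or 0.74 against 0.48 injections.

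**Step 6: the alternative.** With equal follow-up, the sandwich variance of a Poisson log rate is the observed variance divided by n m². It therefore estimates the true variance whichever side of the mean it lies.

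**The case against.** A reader might infer that first-year counts must be under-dispersed, so that the interval will be too wide. The documents do not support that.
- **Stepwise extension is not stated.** The interval rule is in section 5.5.4.1 of the clinical protocol, which the SAP cites but which was not among the documents reviewed. The biweekly grid in SAP 2.8.2.1 and the breakpoint tables (14.2-14, 14.2-15) lean towards 2-week steps, but shell Table 14.2-12 allows all five intervals at Week 12. On the stated intervals alone, V/M can reach 1.34.
- **The bounds describe completers who keep to schedule.** The analysis is on the FAS, with dropout, late visits and missed injections. Simulated dropout mattered little; late visits and missed injections were not modelled.
- **The SAP sentence commits to the 24-month count.** There, lasting differences between patients make over-dispersion likely and the negative binomial is a reasonable choice. SAP 2.8.2.7 leaves the 12-month model optional.
- **The error is conservative and modest in injections**, and the dispersion row would reveal an estimate at zero.

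All of this limits the claim. It does not remove it. Month 12 is a named key secondary endpoint, Table 14.2-9 applies this model to it, and most mixes tried are under-dispersed. A dispersion estimate of zero would show the problem but would not correct the interval, and choosing another variance after seeing it would be a post hoc decision.

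**Conclusion.** The point holds for Month 12 as a probable rather than certain fault. Under the mixes tried, V/M in the first year is below 1 except when patients split towards the 4- and 12-week extremes straight after loading. Where it is below 1, the interval is about 1.1 to 1.9 times too wide. At Month 24 the negative binomial is usually adequate; only a clustering of patients around the middle intervals makes it too wide.

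The size rests on assumed interval mixes, similar dispersion in the two arms and 165 patients per arm. The consequence is lost power and overstated uncertainty for a key secondary endpoint, not a false claim of benefit. The primary BCVA analysis is unaffected. The change is worth making because it is cheap and needs no assumption about the direction of dispersion.

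**What to change.** In SAP 2.8.2.7 and Table 14.2-9, base the standard error, confidence interval and p-value for the injection rate ratio on a variance that is valid in both directions. Use a log-link Poisson model with a log-time offset and a robust (sandwich) variance, or a Pearson-scaled quasi-Poisson. Apply it at least at Month 12 and preferably at both time points, and keep the negative binomial as a sensitivity analysis. State that the Month 12 fit uses follow-up to Month 12 as its offset.

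In the same edit, correct the Binomial Model entry in Table 2.8.2-1, and reconcile the baseline BCVA covariate, which the footnote to Table 14.2-9 includes and SAP 2.8.2.7 omits.

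The cost is one variance option and one SAP sentence. Where counts are over-dispersed, little or no efficiency is lost.

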2.8.2.8 Logistic regression

The logistic regression models to be fitted are detailed in Table 2.8.2.8-1.

Table 2.8.2.8-1 Logistic Regression Models

Model Number	Outcome Variable	Predictor/Covariate	
		Mandatory	Optional
LR_1	Newly developed geographic atrophy between baseline and Month 12 / 24 (Yes/No)	Treatment	Baseline geographic atrophy Baseline IRF/SRF Centre
LR_2	≥ 15 letter increase from baseline to month 24 (Yes/No)	Treatment	Baseline BCVA Centre
LR_3	SRF and IRF at baseline and never resolving SRF at any visit up to Month 2 (Yes/No) Same for Month 12 and 24	Treatment	Baseline IRF/SRF Centre
LR_4	Greater than or equal to 15 letters (EDTRS) gain and less than 15 letters loss from baseline to month 24	Treatment	Baseline BCVA Centre
LR_5	SRF as assessed by the ██████████ CRC and IRF as assessed by Investigators who do not resolve their SRF and IRF by Month 24	Treatment	Baseline IRF/SRF Centre
LR_6	No IRF and SRF at month 2, 12 and 24	Treatment	Baseline IRF/SRF Centre
LR_7	SRF (as assessed by the ██████████ CRC) and IRF (as assessed by Investigators) who do not resolve their SRF and IRF by Month 24	Treatment	Baseline IRF/SRF Centre
LR_8	IRF at baseline who never resolve their IRF at any visit up to Month 2, 12 and 24 (irrespective of SRF)	Treatment	Baseline IRF Centre

Model Number	Outcome Variable	Predictor/Covariate	
		Mandatory	Optional
LR_9	IRF and SRF at baseline who never resolve either their IRF or SRF at any visit up to Month 2, 12 and 24.	Treatment	Baseline IRF/SRF Centre
LR_10	Show $\geq 6/12$ visual acuity at baseline, Month 2, Month 12, month 24	Treatment	Baseline BCVA Centre
LR_11	Show 6/60 visual acuity or worse at baseline, Month 2, Month 12, month 24	Treatment	Baseline BCVA Centre

From each model the adjusted odds ratio for the outcome variable, for intensive compared with relaxed treatment, will be obtained with 2-sided 95% confidence limits.

Using PROC GENMOD to calculate the 95% confidence interval for the odds ratios assumes asymptotic normality of the Wald estimate for the regression coefficient. The 95% confidence interval for the regression parameter of the relaxed regime treatment effect relative to the intensive regime is calculated using an exponential transformation to create the 95% confidence interval for the odds ratio.

All p-values reported on linear hypotheses about regression coefficients will be based on the Wald tests from Type III analyses. In the SAS procedure PROC GENMOD, a Type III analysis will be performed by adding the model options: TYPE3, DIST=BIN, and LINK=LOGIT.

The repeated binary data for absence/Presence of IRF and/or SRF may also be assessed using a random intercept logistic regression (under the frame work of generalized linear mixed model) with robust estimation of SE.

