|               | Intra-retinal Fluid – Center Involvement    | x (xx.x)                    | x (xx.x)                  | x.xxx                            | x (xx.x)                |
|               | No Intra-retinal Fluid – Center Involvement | x (xx.x)                    | x (xx.x)                  | x.xxx                            | x (xx.x)                |
|               | Sub-retinal Fluid                           | x (xx.x)                    | x (xx.x)                  | x.xxx                            | x (xx.x)                |
|               | No Sub-retinal Fluid                        | x (xx.x)                    | x (xx.x)                  | x.xxx                            | x (xx.x)                |
|               | No Intra-retinal Fluid or Sub-retinal Fluid | x (xx.x)                    | x (xx.x)                  | x.xxx                            | x (xx.x)                |
|               | Intra-retinal Fluid OR Sub-retinal Fluid    | x (xx.x)                    | x (xx.x)                  | x.xxx                            | x (xx.x)                |
|               | Intra-retinal Fluid AND Sub-retinal Fluid   | x (xx.x)                    | x (xx.x)                  | x.xxx                            | x (xx.x)                |
| Week n | Intra-retinal Fluid                         | x (xx.x)                    | x (xx.x)                  | x.xxx                            | x (xx.x)                |
|               | No Intra-retinal Fluid                      | x (xx.x)                    | x (xx.x)                  | x.xxx                            | x (xx.x)                |
|               | Sub-retinal Fluid                           | x (xx.x)                    | x (xx.x)                  | x.xxx                            | x (xx.x)                |
| .....         |   |                             |                           |                                  |                         |

**Table 14.2-25 Proportion of patients with SRF at baseline who never resolve their SRF (irrespective of their IRF) – Logistic Regression**

Full Analysis Set

|                     | Intensive
(N=X) | Relaxed
(N=X) |
|---------------------|--------------------|------------------|
| Month 2             | xx (xx.x%)         | xx (xx.x%)       |
| Odds Ratio*         |                    |                  |
| Odds Ratio (95% CI) |                    | x.xx (x.xx,x.xx) |

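### SAP model LR_3 requires both SRF and IRF at baseline, but the exploratory endpoint it should serve covers all patients with baseline SRF, whatever their IRF status

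*SAP*

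**What the plan says.** SAP Section 2.8.1 lists among its exploratory variables one that concerns "patients with SRF at baseline who never resolve their SRF at any visit up to Month 2, 12 and 24 (irrespective of their IRF"). Table 2.8.2-3 repeats it as "Proportion of patients with SRF at baseline who never resolve their SRF at any visit up to Month 2, 12 and 24", again whatever the IRF status, and assigns it to a logistic regression in Section 2.8.2.8. Section 3.1.3 records it as an exploratory endpoint added in the SAP.

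Section 2.8.2.8 then states: "The logistic regression models to be fitted are detailed in Table 2.8.2.8-1". In that table, LR_3 reads "SRF and IRF at baseline and never resolving SRF at any visit up to Month 2 (Yes/No"), with a note that the same applies at Months 12 and 24. Treatment is its mandatory predictor; Baseline IRF/SRF and Centre are optional.

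The table shells (the document supplied as the Protocol) title Table 14.2-25 "Proportion of patients with SRF at baseline who never resolve their SRF (irrespective of their IRF"). It is a logistic regression on the Full Analysis Set at Months 2, 12 and 24, with treatment as factor and baseline BCVA as covariate.

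**The concern.** The endpoint and the model that should analyse it are defined on different patients. The endpoint takes everyone with SRF at baseline. LR_3 adds IRF at baseline as a condition. A programmer working from the SAP model table and one working from the shell would report different proportions and odds ratios under the same title.

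The mismatch falls on a relevant part of the trial. According to the interval-decision definitions under shell Table 14.2-7, the arms share the visual acuity and haemorrhage criteria and both act on any IRF. They differ in how they treat SRF. Persistence of SRF is therefore a natural description of what the two regimens do, and eyes with SRF alone at baseline should be in it.

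**Working it through.** **Step 1: match endpoints to model rows.** The persistent-fluid endpoints of Section 2.8.1 and Table 2.8.2-3 set against Table 2.8.2.8-1:

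| Endpoint | Row in the SAP model table |
|---|---|
| IRF at baseline, never resolved, whatever the SRF | LR_8: "IRF at baseline who never resolve their IRF at any visit up to Month 2, 12 and 24 (irrespective of SRF") |
| Both fluids at baseline, neither resolved | LR_9: "IRF and SRF at baseline who never resolve either their IRF or SRF at any visit up to Month 2, 12 and 24" |
| SRF (reading centre) and IRF (investigator), unresolved by Month 24 | LR_5: "IRF as assessed by Investigators who do not resolve their SRF and IRF by Month 24"; LR_7 repeats it |
| SRF at baseline, never resolved, whatever the IRF | none |

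LR_3 matches none of the listed endpoints. LR_8 is the IRF counterpart and shows how the SRF row would be expected to read. LR_5 and LR_7 have the same visible words apart from brackets (the reading centre's name is blacked out in both) and the same covariates.

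**Step 2: what LR_3 does if followed.** Its wording allows two readings.
- As a restricted population: eyes with SRF but no IRF at baseline are left out.
- As a Yes/No outcome over a wider set of patients: those eyes are included, but if their SRF never resolves they are coded No, because the IRF condition fails.

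Neither reading gives the listed endpoint.

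**Step 3: scale, for illustration.** The documents give no cross-tabulation of baseline SRF and IRF, so only bounds are possible. The example totals in shell Table 14.1-10 (N = 347) are:
- SRF present, reading centre: S = 286 (82.4%)
- IRF present, reading centre: 130 (37.5%)
- IRF or intra-retinal cyst, reading centre: 214 (61.7%)
- IRF present, CRF: 268 (77.2%)

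With I the IRF count, the number with both fluids lies between max(0, S + I − N) and min(S, I). Eyes with SRF only are S minus that number.

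| IRF count used | Both fluids | SRF only | Share of 286 |
|---|---|---|---|
| Reading-centre IRF, 130 | 286 + 130 − 347 = 69 to 130 | 156 to 217 | 54.5% to 75.9% |
| Reading-centre IRF or cyst, 214 | 286 + 214 − 347 = 153 to 214 | 72 to 133 | 25.2% to 46.5% |
| CRF IRF, 268 | 286 + 268 − 347 = 207 to 268 | 18 to 79 | 6.3% to 27.6% |

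If CRF data were used for both fluids (SRF 271, IRF 268), the bounds would be 271 − 268 = 3 (1.1%) and 271 − (271 + 268 − 347) = 79 (29.2%) of 271. SAP Section 2.1 assigns reading-centre data to efficacy analyses, which favours the first two rows of the table. The third row uses the mixed sources that the SAP names for its combined SRF and IRF endpoint.

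**The case against.** The strongest reply is that the intended population is not in doubt. Section 2.8.1, Table 2.8.2-3, Section 3.1.3 and shell Table 14.2-25 all agree, and one row is mis-worded. The shell also specifies a logistic model for the right patients at the right times. This stands as far as it goes. A reader might infer that the endpoint has no correct model anywhere, and the documents do not support that; the gap is in the SAP model table. The shell does not close it, because the SAP names its own table as the list of models to be fitted, and the shell's baseline BCVA covariate does not appear in LR_3.

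Three other stronger readings also fail.
- A reader might take the LR_5/LR_7 repetition as the cause of the gap. It concerns a different endpoint, and fitting the same model twice gives the same answer. It shows only that neither row fills the gap.
- A reader might say that LR_3 removes exactly the eyes on which the arms differ. The SRF rule is applied at interval decisions after baseline, so an eye with both fluids at baseline whose IRF later clears is also subject to it. LR_3 loses informative eyes, but not all of them and not only them.
- A reader might quote 55% as the size of the problem. That is the minimum under one of several IRF counts. Notes on several efficacy figures, such as Figures 14.2-13 and 14.2-18, group IRF with cysts, which lowers the minimum to 25%; CRF-reported IRF lowers it to 6%.

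The counts themselves are weak evidence. The same 252 and 95 columns appear under treatment in Table 14.1-10 and under genotype-sample status in Table 14.1-11, and a 252:95 split does not fit the 1:1 randomisation in SAP Section 1. At least one of those tables carries pasted example data.

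**Conclusion.** LR_3 is wrong as written. It imposes a baseline IRF condition that the endpoint excludes, and no other row of SAP Table 2.8.2.8-1 models the endpoint. This conclusion rests on the text alone and does not depend on any count.

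The size does depend on the counts. Taking the shell totals at face value, and reading-centre SRF as the denominator, at least 6%, 25% or 55% of the 286 SRF-positive eyes would be excluded or open to miscoding, according to whether IRF means CRF IRF, reading-centre IRF or cyst, or reading-centre IRF alone. These are lower bounds from figures that may be placeholders, and the true share could be outside them.

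The endpoint is exploratory. The primary BCVA non-inferiority analysis is unaffected.

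**What to change.** Reword the LR_3 outcome so that it reads, like Section 2.8.1, as SRF present at baseline and not resolved at any visit up to Month 2, 12 or 24, whatever the IRF status. State that the denominator is all FAS patients with baseline SRF, so that the row cannot be read as an outcome coded over everyone.

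Reconcile the covariates with shell Table 14.2-25. The shell fits treatment plus baseline BCVA; LR_3 offers Baseline IRF/SRF and Centre as options and omits baseline BCVA. One set should be chosen and stated in both documents. If Baseline IRF/SRF means presence or absence, its SRF part is constant once the population is limited to patients with baseline SRF.

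Separately, as an editorial tidy-up, delete either LR_5 or LR_7.

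The cost is one reworded row, one covariate decision carried into the SAP and the shell, and one deleted row. Data collection, sample size and the primary analysis do not change.
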